10.2 Operating Characteristics of Clinical Trial Design

The operating characteristics of the multi-stage adaptive design were illustrated in a 10,000-iteration simulation. The simulations employed the assumptions outlined above (unselected population study: alpha 0.10, power 0.90, $H_0 = 0.1$, $H_1 = 0.3$; selected population study: alpha 0.10, power 0.80, $H_0 = 0.3$, $H_1 = 0.6$) in a 50 subject study.

10.2.1 Estimation of Type 1 Error

Assuming that the response rates for all-comers is 0.1 and the response rate for the biomarker selected population is 0.3 (both null hypotheses), estimates for type 1 error were generated using the simulation. Two scenarios are presented: prevalence of biomarker positive subjects of 10% and 15% in the population.

Scenario	N Stage 1	N Stage 2	N Enriched	N Total	$\geq N$ to Reject Stage 1	$\geq N$ to Reject Stage 2	Type 1 Error All-comers	Type 1 Error Biomarker+	Type 1 Error Combined
10% Biomarker +	20	10	20	50	3	6	0.07	0.04	0.11
15% Biomarker +	20	10	20	50	3	6	0.07	0.03	0.10

The proportion of trials that are stopped for futility in this simulation, with or without enrichment, is presented below:

Scenario	Stage 1 Futility No Enrichment	Stage 2 Futility No Enrichment	Enrichment Futility

10% Biomarker +	0.09	0.03	0.78
15% Biomarker +	0.15	0.03	0.72

10.2.2 Estimation of Power

Assuming that the response rates for all-comers is 0.3 and the response rate for the biomarker selected population is 0.6 (both alternative hypotheses), estimates for power were generated using the simulation. Two scenarios are presented: prevalence of biomarker positive subjects of 10% and 15% in the population.

Scenario	N Stage 1	N Stage 2	N Enriched	N Total	≥N to Reject Stage 1	≥N to Reject Stage 2	Power All-comers	Power Biomarker+	Power Combined
10% Biomarker +	20	10	20	50	3	6	0.92	0.07	0.98
15% Biomarker +	20	10	20	50	3	6	0.91	0.07	0.98

The proportion of trials that are stopped for futility in this simulation, with or without enrichment, is presented below:

Scenario	Stage 1 Futility No Enrichment	Stage 2 Futility No Enrichment	Enrichment Futility
10% Biomarker +	0.00	0.00	0.01
15% Biomarker +	0.00	0.01	0.01

10.2.3 Estimation of Power (in case enrichment is needed to demonstrate efficacy)

Assuming that the response rates for all-comers is 0.1 and the response rate for the biomarker selected population is 0.6 (null in all-comer, alternative in selected), estimates for power were generated using the simulation. Two scenarios are presented: prevalence of biomarker positive subjects of 10% and 15% in the population.

Scenario	N Stage 1	N Stage 2	N Enriched	N Total	≥N to Reject Stage 1	≥N to Reject Stage 2	Power All-comers	Power Biomarker+	Power Combined
----------	--------------	--------------	---------------	------------	----------------------------	----------------------------	---------------------	---------------------	-------------------

10% Biomarker +	20	10	20	50	3	6	0.07	0.80	0.87
15% Biomarker +	20	10	20	50	3	6	0.07	0.79	0.86

The proportion of trials that are stopped for futility in this simulation, with or without enrichment, is presented below:

Scenario	Stage 1 Futility No Enrichment	Stage 2 Futility No Enrichment	Enrichment Futility
10% Biomarker +	0.02	0.00	0.12
15% Biomarker +	0.02	0.00	0.12

10.2.3 Estimation of Power with variable assumptions of response rates for subpopulations
 The probably of response in the all-comer population is varied from 0.05 to 0.30 and 0.20-0.60 in the biomarker-selected population.

Scenario #	Resp. Rate Biomarker-	Resp. Rate Biomarker+	Resp. Rate All-comer	Proportion Biomarker+	Power All-comers	Power Biomarker+	Power Combined
1	0.03	0.20.20	0.05 0.05	0.10 0.100.00	0.000	00000	0.00
2	0.09	0.20.20	0.10 0.10	0.10 0.100.07	0.000	00000	0.07
3	0.14	0.20.20	0.15 0.15	0.10 0.100.27	0.000	00200	0.27
4	0.20	0.20.20	0.20 0.20	0.10 0.100.55	0.550	00550	0.55
5	0.26	0.20.20	0.25 0.25	0.10 0.100.78	0.780	00780	0.78
6	0.31	0.20.20	0.30 0.30	0.10 0.100.91	0.900	00900	0.91
7	0.02	0.30.30	0.05 0.05	0.10 0.100.00	0.004	00004	0.05
8	0.08	0.30.30	0.10 0.10	0.10 0.100.07	0.004	00104	0.11
9	0.13	0.30.30	0.15 0.15	0.10 0.100.27	0.203	00303	0.30
10	0.19	0.30.30	0.20 0.20	0.10 0.100.55	0.552	00552	0.56
11	0.24	0.30.30	0.25 0.25	0.10 0.100.78	0.781	00781	0.79
12	0.30	0.30.30	0.30 0.30	0.10 0.100.91	0.900	00900	0.91
13	0.01	0.40.40	0.05 0.05	0.10 0.100.00	0.003	00003	0.23
14	0.07	0.40.40	0.10 0.10	0.10 0.100.07	0.021	00211	0.28
15	0.12	0.40.40	0.15 0.15	0.10 0.100.27	0.216	00416	0.43
16	0.18	0.40.40	0.20 0.20	0.10 0.100.54	0.540	00640	0.64
17	0.23	0.40.40	0.25 0.25	0.10 0.100.78	0.784	00804	0.82
18	0.29	0.40.40	0.30 0.30	0.10 0.100.91	0.902	00902	0.93

19	0.00	0.50.50	0.05	0.05	0.10	0.100.00	0.056	00556	0.57
20	0.06	0.50.50	0.10	0.10	0.10	0.100.07	0.052	00552	0.59
21	0.11	0.50.50	0.15	0.15	0.10	0.100.27	0.241	00681	0.68
22	0.17	0.50.50	0.20	0.20	0.10	0.100.55	0.525	00825	0.80
23	0.22	0.50.50	0.25	0.25	0.10	0.100.78	0.782	00902	0.90
24	0.28	0.50.50	0.30	0.30	0.10	0.100.91	0.904	00904	0.96
25	0.04	0.60.60	0.10	0.10	0.10	0.100.07	0.080	00830	0.87
26	0.10	0.60.60	0.15	0.15	0.10	0.100.28	0.282	00962	0.90
27	0.16	0.60.60	0.20	0.20	0.10	0.100.54	0.549	00939	0.93
28	0.21	0.60.60	0.25	0.25	0.10	0.100.78	0.788	00968	0.96
29	0.27	0.60.60	0.30	0.30	0.10	0.100.91	0.908	00988	0.98
30	0.02	0.20.20	0.05	0.05	0.15	0.150.00	0.000	00000	0.00
31	0.08	0.20.20	0.10	0.10	0.15	0.150.07	0.010	00000	0.07
32	0.14	0.20.20	0.15	0.15	0.15	0.150.27	0.210	00200	0.27
33	0.20	0.20.20	0.20	0.20	0.15	0.150.55	0.550	00550	0.55
34	0.26	0.20.20	0.25	0.25	0.15	0.150.78	0.780	00780	0.78
35	0.32	0.20.20	0.30	0.30	0.15	0.150.91	0.900	00910	0.91
36	0.01	0.30.30	0.05	0.05	0.15	0.150.00	0.004	00004	0.04
37	0.06	0.30.30	0.10	0.10	0.15	0.150.07	0.014	00104	0.10
38	0.12	0.30.30	0.15	0.15	0.15	0.150.28	0.283	00303	0.30
39	0.18	0.30.30	0.20	0.20	0.15	0.150.55	0.551	00551	0.56
40	0.24	0.30.30	0.25	0.25	0.15	0.150.78	0.781	00781	0.78
41	0.30	0.30.30	0.30	0.30	0.15	0.150.91	0.900	00910	0.91
42	0.05	0.40.40	0.10	0.10	0.15	0.150.07	0.020	00220	0.27
43	0.11	0.40.40	0.15	0.15	0.15	0.150.27	0.215	00415	0.42
44	0.16	0.40.40	0.20	0.20	0.15	0.150.55	0.559	00609	0.64
45	0.22	0.40.40	0.25	0.25	0.15	0.150.77	0.774	00814	0.81
46	0.28	0.40.40	0.30	0.30	0.15	0.150.91	0.901	00921	0.92
47	0.03	0.50.50	0.10	0.10	0.15	0.150.07	0.032	00552	0.59
48	0.09	0.50.50	0.15	0.15	0.15	0.150.28	0.289	00639	0.67
49	0.15	0.50.50	0.20	0.20	0.15	0.150.55	0.554	00724	0.79
50	0.21	0.50.50	0.25	0.25	0.15	0.150.78	0.781	00891	0.89
51	0.26	0.50.50	0.30	0.30	0.15	0.150.91	0.904	00954	0.95
52	0.01	0.60.60	0.10	0.10	0.15	0.150.07	0.079	00869	0.86
53	0.07	0.60.60	0.15	0.15	0.15	0.150.28	0.281	00891	0.89
54	0.13	0.60.60	0.20	0.20	0.15	0.150.55	0.538	00938	0.93
55	0.19	0.60.60	0.25	0.25	0.15	0.150.78	0.788	00968	0.96
56	0.25	0.60.60	0.30	0.30	0.15	0.150.91	0.907	00987	0.98

The proportion of trials that are stopped for futility for these simulations, with or without enrichment, is presented below:

Scenario #	Stage 1 Futility No Enrichment	Stage 2 Futility No Enrichment	Enrichment Futility
1	0.15	0.01	0.84
2	0.12	0.05	0.76
3	0.08	0.08	0.56
4	0.05	0.08	0.32
5	0.03	0.05	0.15
6	0.01	0.02	0.05
7	0.10	0.00	0.85
8	0.08	0.03	0.78
9	0.06	0.05	0.59
10	0.04	0.05	0.35
11	0.02	0.03	0.16
12	0.01	0.02	0.06
13	0.06	0.00	0.71
14	0.05	0.01	0.65
15	0.04	0.03	0.50
16	0.02	0.03	0.30
17	0.01	0.02	0.14
18	0.01	0.01	0.06
19	0.03	0.00	0.40
20	0.03	0.00	0.38
21	0.02	0.01	0.28
22	0.01	0.02	0.17
23	0.01	0.01	0.08
24	0.00	0.01	0.03
25	0.01	0.00	0.11
26	0.01	0.00	0.09
27	0.01	0.01	0.05
28	0.00	0.01	0.02
29	0.00	0.00	0.01
30	0.28	0.01	0.71
31	0.23	0.07	0.62
32	0.16	0.13	0.43
33	0.09	0.12	0.24
34	0.05	0.07	0.10
35	0.02	0.04	0.03
36	0.18	0.00	0.78
37	0.16	0.03	0.71
38	0.11	0.08	0.51
39	0.07	0.08	0.29

40	0.03	0.05	0.13
41	0.02	0.03	0.05
42	0.09	0.01	0.63
43	0.07	0.04	0.47
44	0.05	0.04	0.27
45	0.03	0.03	0.13
46	0.01	0.02	0.05
47	0.05	0.00	0.36
48	0.04	0.01	0.28
49	0.03	0.02	0.16
50	0.02	0.02	0.08
51	0.01	0.01	0.03
52	0.02	0.00	0.11
53	0.02	0.00	0.09
54	0.01	0.01	0.05
55	0.01	0.01	0.02
56	0.01	0.01	0.01

10.3 Analysis Populations

10.3.1 *Evaluable population*

All patients who meet eligibility criteria and receive at least 1 dose of study medication will be included in the primary analysis of the response rate, even if there are major protocol deviations (eg, incorrect treatment schedule or drug administration). Each patient will be assigned to one of the following categories:

Conclusions are to be based on the population of all eligible patients. Supportive analysis and sensitivity analysis may be performed on various subsets of patients, such as those with no major protocol deviations or those who continued in the study for the entire treatment period (ie, did not withdraw prematurely). Subanalyses will not serve as the basis for drawing conclusions concerning treatment efficacy.

10.3.2 *Safety population*

All patients enrolled in the study will be included in the safety analysis population and considered evaluable for toxicity and safety from the time of their first dose. Demographic and baseline characteristics for the safety population will be summarized by number and percent for categorical data (eg, sex, race/ethnicity) and by descriptive statistics for continuous data (eg, weight, vital signs, EKG readings, disease status).

10.4 Safety Analysis

10.4.1 *Evaluation of adverse events*

Treatment-emergent adverse events will be translated from investigator terms to MedDRA v6.0 terminology and summarized (number and percentage of patients) for all patients who receive at least 1 dose. Adverse event summaries will be organized by body system, frequency of occurrence, intensity (ie, severity grade), and causality or attribution. Patients who experience an adverse event more than once will be counted only once. The occurrence with the maximum severity will be used to calculate intensity.

10.4.2 *Evaluation of serious adverse events and premature withdrawals*

Adverse events deemed serious and those resulting in treatment withdrawal or death will be summarized separately. Narrative paragraphs will be generated to describe the circumstances surrounding each SAE and death.

10.4.3 *Evaluation of laboratory parameters and assays*

Selected clinical laboratory parameters will be summarized and clinically significant changes from baseline will be discussed.

10.4.4 *Extent of exposure*

Treatment exposure will be summarized for all patients, including dose administration, number of cycles, dose modifications or delays, and duration of therapy.

11. PROTECTION OF HUMAN SUBJECTS

11.1 Ethical Considerations

This study will be conducted in compliance with the protocol, GCP guidelines established by the International Conference on Harmonisation, and the ethical standards set forth in the Declaration of Helsinki 2004 (available at: www.laakariliitto.fi/e/ethics/helsinki.html).

11.2 Protocol Amendments

Before starting the study, the protocol must be approved by each institution's IRB or Independent Ethics Committee (IEC). Amendments to the protocol may be made only with consent of the lead site/sponsor and principal investigator and are subject to IRB approval before instituting.

11.3 Written Informed Consent

Before obtaining consent, members of the study team will review the rationale for the treatment program with the patient. The discussion will review the alternatives available (including hormonal therapy, chemotherapy, or supportive care as appropriate), the potential benefits of this program, the risks and the probability of their occurrence, and the procedures to minimize these risks. Should an adverse event occur, the provisions available to ensure medical intervention will also be reviewed. Why the risks are reasonable in relation to the anticipated benefits, incentives, or costs that will or may be incurred as a result of participating in the study, as well as the efforts to maintain confidentiality, will also be discussed with the patient.

Patients will be required to sign and date (in triplicate) a statement of informed consent that meets the requirements of the Code of Federal Regulations (Federal Register Vol. 46, No. 17, January 27, 1981, part 50) and the IRB. The medical record will include a statement that written informed consent was obtained (and document the date that it was obtained) before the patient is enrolled in the study. The original signed document will become part of the patient's medical record, a copy will be forwarded to the lead site/sponsor pursuant to sponsor registration and to the PCCTC coordinating center at MSKCC, and a copy will be sent home with each patient.

The consent form will include the following:

- the nature and objectives, potential toxicities, and benefits of the intended study
- the length of therapy and likely follow-up required
- alternatives to the proposed therapy (including available standard and investigational therapies)
- the name of the investigator(s) responsible for the protocol
- the right of the patient to accept or refuse treatment and to withdraw from participation in this study
- Text regarding the consortium and the coordinating center should be added to all institutional informed consent documents and sections in the research authorization/HIPAA forms (eg, "Prostate Cancer Clinical Trial Consortium, Coordinating Center at Memorial Sloan-Kettering Cancer Center, New York, NY")

11.4 Protection of Privacy

Patients will be informed of the extent to which their confidential health information generated from this study may be used for research purposes. After this discussion, they will be asked to sign a Notice of Privacy Practice research authorization/HIPAA form. The original signed documents will become part of the patient's medical records, and each patient will receive a copy of the signed documents. The use and disclosure of protected health information will be limited to the individuals described in the research authorization form. The research authorization form must be completed by the principal investigator and approved by the IRB.

11.5 Terminating or Modifying the Study

Adverse event and laboratory data from this trial will be assessed by the medical monitor ([name] [name]) on an ongoing basis. At least quarterly, data from the clinical database will be reviewed. The results of this review will be shared with all investigators either in writing or as part of a teleconference. SAEs will be reviewed as they are reported to the lead site/sponsor, and the medical monitor will make an assessment regarding the safety of continuing or modifying the study. This assessment will be shared with the investigators either in writing or as part of a teleconference. Should the assessment of either the lead site/sponsor or the principal investigator be that the study should be terminated, the study will be closed to further accrual. Patients who are receiving olaparib will be assessed individually by the investigator to see if it is in the patients' best interest to continue, which might be the case for a patient that is responding to the intervention. Follow-up safety assessments will be performed for all patients who are terminated from the study prematurely.

APPENDIX A: PERFORMANCE STATUS CRITERIA

ECOG Performance Status Scale		Karnofsky Performance Scale	
Grade	Description	%	Description
0	Normal activity. Fully active, able to continue all predisease performance without restriction.	100	Normal, no complaints, no evidence of disease
		90	Able to carry on normal activity, minor signs or symptoms of disease
1	Symptoms, but ambulatory. Restricted in physically strenuous activity but ambulatory and able to carry out work of a light or sedentary nature (eg, light housework, office work).	80	Normal activity with effort, some signs or symptoms of disease
		70	Cares for self, unable to carry on normal activity or to do active work
2	In bed <50% of the time. Ambulatory and capable of all self-care but unable to carry out any work activities. Up and about more than 50% of waking hours.	60	Requires occasional assistance but is able to care for most needs
		50	Requires considerable assistance and frequent medical care
3	In bed >50% of the time. Capable of only limited self-care, confined to bed or chair >50% of waking hours.	40	Disabled, requires special care and assistance
		30	Severely disabled, hospitalization indicated. Death not imminent.
4	100% bedridden. Completely disabled, cannot carry on any self-care, totally confined to bed or chair.	20	Very sick, hospitalization indicated. Death not imminent.
		10	Moribund, fatal processes progressing rapidly
5	Dead	0	Dead

APPENDIX B: MEDICATIONS WITH THE POTENTIAL FOR DRUG-DRUG INTERACTIONS

Class	Agents
Strong CYP3A inhibitors	e.g. itraconazole, telithromycin, clarithromycin, ketoconazole, voriconazole, nefazodone, posaconazole, ritinovir, lopinavir/ritinovir, indinavir, saquinavir, nelfinavir, boceprevir, telaprevir
Moderate CYP3A inhibitors	e.g. amprenavir, aprepitant, atazanavir, ciprofloxacin, daaunavir/ritonavir, diltiazem, erythromycin, fluconazole, fosamprenavir, verapamil
Strong CYP3A Inducers	e.g. phenobarbital, phenytoin, rifampicin, rifabutin, rifapentine, carbamazepine, nevirapine and St John's Wort

APPENDIX D: GLOSSARY OF ABBREVIATIONS AND ACRONYMS

ADR	adverse drug reaction
ADT	androgen-deprivation therapy
AE	adverse event
ANC	absolute neutrophil count
AUC	area under the plasma concentration-time curve
bid	bis in die (twice a day)
BMI	body mass index
BP	blood pressure
C	Celsius
CBC	complete blood count
Crcl	creatinine clearance
CRF	case report form
CRMIS	Clinical Research Management Information System
CRPC	castration resistant prostate cancer
CT	computerized tomography
CTC	circulating tumor cell
CTCAE	Common Terminology Criteria for Adverse Events
CYP	cytochrome p-450
dL	deciliter
ECOG	Eastern Cooperative Oncology Group
GCP	good clinical practice
HIPAA	Health Insurance Portability and Accountability Act
IND	investigational new drug
IRB	Institutional Review Board
PFS	progression-free survival
PI	principal investigator
PO	per os (by mouth)
PSA	prostate-specific antigen
PSA-DT	prostate-specific antigen doubling time

APPENDIX E. ACCEPTABLE BIRTH CONTROL METHODS

Olaparib is regarded as a compound with medium/high fetal risk. Subjects with partners of childbearing potential, who are sexually active, must agree to the use of TWO highly effective forms of contraception in combination [as listed below], throughout the period of taking study treatment and for at least 1 month after last dose of study drug(s), or they must totally/truly abstain from any form of sexual intercourse (see below).

Acceptable Non-hormonal birth control methods include:

- Total sexual abstinence. Abstinence must continue for the total duration of study treatment and for at least 1 month after the last dose. Periodic abstinence (eg, calendar ovulation, symptothermal post ovulation methods) and withdrawal are not acceptable methods of contraception.
- Vasectomised sexual partner PLUS male condom. With participant assurance that partner received post-vasectomy confirmation of azoospermia.
- Tubal occlusion PLUS male condom
- IUD PLUS male condom. Provided coils are copper-banded

Acceptable hormonal methods:

- Normal and low dose combined oral pills PLUS male condom
- Cerazette (desogestrel) PLUS male condom. Cerazette is currently the only highly efficacious progesterone based pill.
- Hormonal shot or injection (eg., Depo-Provera) PLUS male condom
- Etonogestrel implants (e.g., Implanon, Norplant) PLUS male condom
- Norelgestromin / EE transdermal system PLUS male condom
- Intrauterine system [IUS] device (eg., levonorgestrel releasing IUS -Mirena®) PLUS male condom
- Intravaginal device (e.g., EE and etonogestrel) PLUS male condom

APPENDIX F. ACTIONS REQUIRED IN CASES OF COMBINED INCREASE OF AMINOTRANSFERASE AND TOTAL BILIRUBIN – HY'S LAW

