 - Total bilirubin $\leq 1.5 \times$ institutional upper limit of normal (ULN)
 - Aspartate aminotransferase (AST) (Serum Glutamic Oxaloacetic Transaminase (SGOT)) / Alanine aminotransferase (ALT) (Serum Glutamic Pyruvate Transaminase (SGPT)) $< 2.5 \times$ institutional upper limit of normal

Note: Patients with elevations in bilirubin, AST, or ALT should be thoroughly evaluated for the etiology of this abnormality prior to entry and patients with evidence of viral infection should be excluded.

- Patients must have creatinine clearance estimated using the Cockcroft-Gault equation of ≥ 51 mL/min:
Estimated creatinine clearance = $\frac{(140 - \text{age [years]}) \times \text{weight (kg)}}{\text{serum creatinine (mg/dL)} \times 72}$

9. Eastern Cooperative Oncology Group (ECOG) performance status 0-1 (see Appendix A).
10. Male participants and their partners, who are sexually active and of childbearing potential, must agree to the use of two highly effective forms of contraception in combination [see appendix E for acceptable methods], throughout the period of taking study treatment and for 3 months after last dose of study drug to prevent pregnancy in a partner.
11. *For enrichment stage of trial only (if necessary):* Confirmation of a suspected/known deleterious mutation in a gene of interest (ATM, BARD1, BRCA1, BRCA2, BRIP1, CDK12, CHEK1, CHEK2, FANCL, PALB2, PPP2R2A, RAD51B, RAD51C, RAD51D, or other DNA repair genes) via CLIA certified testing.

Exclusion:

1. Prior ADT in the past 6 months. Prior ADT in context of neoadjuvant/adjuvant primary; prior ADT for biochemical recurrence is allowed, as long as no ADT has been administered in past 6 months and testosterone has recovered (>150 ng/dl). The total duration of prior ADT should not exceed 24 months.

2. Prior oral anti-androgen (e.g. bicalutamide, nilutamide, enzalutamide, apalutamide), or androgen synthesis inhibitor (e.g. abiraterone, orteronel) in the past 6 months. 5-alpha reductase inhibitor therapy (e.g. finasteride, dutasteride) is allowed, as long as subject has been stable on medication for past 6 months.
3. Prior treatment with intravenous chemotherapy for prostate cancer.
4. Involvement in the planning and/or conduct of the study (applies to both AstraZeneca staff and/or staff at the study site)
5. Participation in another clinical study with an investigational product during the last 1 month.
6. Any previous treatment with PARP inhibitor, including olaparib.

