Note: Patients with creatinine clearance between 51- 80 mL/min either at trial enrolment or during the course of the trial should be monitored every 2 weeks for laboratory assessment and toxicity evaluation.

- ECOG PS ≤ 1 . (Appendix A: Performance Status Criteria)
- Participants must have a life expectancy ≥ 16 weeks.

- Male participants and their partners, who are sexually active and of childbearing potential, must agree to the use of two highly effective forms of contraception in combination [see appendix E for acceptable methods], throughout the period of taking study treatment and for 3 months after last dose of study drug to prevent pregnancy in a partner.
- *For enrichment stage of trial only (if necessary):* Confirmation of a suspected/known deleterious mutation in a gene of interest (ATM, BARD1, BRCA1, BRCA2, BRIP1, CDK12, CHEK1, CHEK2, FANCL, PALB2, PPP2R2A, RAD51B, RAD51C, RAD51D or other DNA repair genes) via CLIA certified testing.

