5.6 End of Treatment/Treatment Discontinuation Visit (28 days after last dose ±3 days)

- conduct physical exam (including vital signs, height/weight)
- perform laboratory tests: Complete blood count w/Diff, PSA, Comprehensive metabolic panel
- assess performance status (ECOG). (Appendix A)
- review concurrent medications
- assess AEs
- if patient is discontinuing participation in study, perform radiographic tests: CT A/P and NM Bone Scan (if these have not been performed in the prior 3 months)

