5.10 Contraception

Patients with partners of child bearing potential, who are sexually active, must agree to the use of two highly effective forms of contraception throughout period of taking study treatment and for 3 months after last dose of study drug.

For details refer to Appendix E Acceptable Birth Control Methods.

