Disability is a substantial disruption of the patient's ability to conduct normal life functions.

7.1.8 *Pregnancy*

Male participants should refrain from fathering a child or donating sperm during the study and for 3 months following the last dose.

Pregnancy of the patient's partners is not considered to be an adverse event. However, the outcome of all pregnancies (spontaneous miscarriage, elective termination, ectopic pregnancy, normal birth or congenital abnormality) should if possible be followed up and documented.

The outcome of any conception occurring from the date of the first dose until 3 months *after the last dose* should be followed up and documented.

All outcomes of pregnancy should be reported to AstraZeneca.

7.1.9 *Medical significance*

An event that is not fatal or life-threatening and that does not necessitate hospitalization may be considered serious if, in the opinion of the investigator, it jeopardizes the patient's status and might lead to medical or surgical intervention to prevent any of the above outcomes. Such medically significant events could include allergic bronchospasm requiring intensive treatment in the emergency room or at home, blood dyscrasias that do not result in inpatient hospitalization, or the development of drug dependency or abuse.

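### Appendix E sets a 1-month post-treatment minimum for contraception and abstinence, while the rest of the protocol requires 3 months

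*Combined protocol and SAP*

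**What the plan says.** Appendix E states the duration twice, both times as a requirement. For contraception it asks for two methods in combination "throughout the period of taking study treatment and for at least 1 month after last dose of study drug(s"). For abstinence it says: "Abstinence must continue for the total duration of study treatment and for at least 1 month after the last dose".

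The other sections that state the duration give 3 months. Section 3.3 requires agreement to two highly effective methods "throughout the period of taking study treatment and for 3 months after last dose of study drug to prevent pregnancy in a partner". The synopsis (inclusion criterion 10) and the eligibility text repeated in Section 5.1 say the same. All three point to the appendix only for the list of methods: "see appendix E for acceptable methods". Section 5.10 gives 3 months and then adds: "For details refer to Appendix E Acceptable Birth Control Methods".

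Section 7.1.8 takes the same period from the pregnancy side: "Male participants should refrain from fathering a child or donating sperm during the study and for 3 months following the last dose". It also requires follow-up of conceptions over that window: "The outcome of any conception occurring from the date of the first dose until 3 months" after the last dose.

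**The concern.** One protocol sets two different minimums for the same obligation, and the shorter one sits where the methods are listed. Appendix E is the natural page for a site to counsel from, and Section 5.10 directs the reader there. It is also the only place that names abstinence as an option, so a man choosing abstinence finds the 1-month figure beside his method.

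What is at stake is an instruction to participants about fetal exposure. The same appendix classes olaparib as carrying medium to high fetal risk. A participant told 1 month would believe he had complied while still inside the period in which Section 7.1.8 asks him not to father a child or donate sperm. The statistical design does not depend on this.

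**Working it through.** The plan gives no calculated figure to reproduce. The check sets the statements side by side.

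| Place | Obligation | Period after last dose |
|---|---|---|
| Synopsis, inclusion 10 | Two contraceptive methods | 3 months |
| Section 3.3 | Two contraceptive methods | 3 months |
| Section 5.1 (eligibility text repeated) | Two contraceptive methods | 3 months |
| Section 5.10 | Two contraceptive methods | 3 months |
| Section 7.1.8 | No fathering of a child, no sperm donation; conception follow-up | 3 months |
| Appendix E, opening paragraph | Two contraceptive methods | At least 1 month |
| Appendix E, abstinence | Total abstinence | At least 1 month |

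**Size of the gap.** 3 months − 1 month = 2 months.

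**Can the two be reconciled?** Appendix E sets a floor, so a man who continues for 3 months satisfies every section. The reverse fails. A man who stops at 5 weeks satisfies Appendix E and breaches Sections 3.3 and 5.10. Two different floors for one obligation are inconsistent.

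**Which figure is intended?** All five places outside Appendix E give 3 months, and Section 7.1.8 bases its conception follow-up on that period. The 3-month figure is therefore the one to keep.

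**Would a later visit catch the error?** Section 5.6 is titled "End of Treatment/Treatment Discontinuation Visit (28 days after last dose ±3 days"). That is day 28 − 3 = 25 to day 28 + 3 = 31 after the last dose, about when the Appendix E minimum ends and about 2 months before the 3-month period ends. Section 5.7 continues 28-day visits for men withdrawn because of adverse events, and the study calendar continues monthly follow-up until toxicities settle. For a man with no ongoing adverse event, Section 5 schedules nothing in the remaining 2 months.

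**The case against.** The strongest reply is that the governing text is already clear. The eligibility criterion is what the participant agrees to, and it states 3 months itself, using the appendix only as a list of methods. Section 5.10 gives 3 months before it mentions Appendix E, so a reader taking that route sees the right figure first. A man who stopped at 1 month would be breaching what he agreed to. This lowers the risk but does not remove the conflict, because a site that uses Appendix E alone still gives the wrong instruction.

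Three narrower points have some force:

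- **Abstinence.** Section 7.1.8 applies to every male participant whatever his method, and the 3 months in the eligibility criterion can be read as covering every method in the appendix. It would be too strong to say that no 3-month rule reaches abstinence. What stands is that Appendix E alone names abstinence and pairs it with 1 month.
- **Visit timing.** The Section 5.6 visit lists no contraception review, so its closeness to the 1-month mark does not itself show harm. Sections 5.9 and 7.4.3 also imply some later contact, for subsequent cancer therapy and survival, although Section 5 does not schedule it. Timing is supporting context only.
- **Count.** The Section 5.1 text repeats Section 3.3 and is not a separate statement. Leaving it out gives four places instead of five, all still at 3 months.

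The consent form was not available to check, so the written instruction that participants receive is unknown.

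**Conclusion.** The concern holds. Appendix E is wrong as written: both of its statements set a minimum 2 months shorter than the rest of the protocol. This is an internal inconsistency in a safety instruction, and it should be corrected.

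The practical effect is probably small. The rule applies only to sexually active men with partners of childbearing potential, in a trial where every participant has had a prostatectomy. The documents do not say how many men that is. The eligibility agreement and the conception follow-up already run to 3 months. The primary endpoint, power, type I error and planned analyses are unaffected.

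The conclusion assumes that 3 months is the intended period, which the agreement of all the other sections supports.

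**What to change.** In Appendix E, replace the 1-month minimum with 3 months after the last dose in both places: the opening contraception paragraph and the abstinence entry. Confirm that the consent form and any counselling sheet given to participants also say 3 months.

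The cost is two phrases at the next amendment and one check of the consent text. Design, sample size and analysis do not change.
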